3. STUDY DESIGN

3.1 DESCRIPTION OF THE STUDY

This is an open-label, phase I/II trial, which will assess the safety, tolerability and efficacy of a treat and extend management protocol for DME. Eyes which meet screening criteria will be enrolled into one of three treatment groups: (1) monthly intravitreal injections of 0.3 mg ranibizumab (Monthly Cohort, 30 eyes); (2) monthly intravitreal injections of 0.3 mg ranibizumab for 4 visits, followed by a “Treat and Extend” protocol based on pre-specified criteria of disease activity (T-REX cohort, 60 eyes); (3) monthly intravitreal injections of 0.3 mg ranibizumab for 4 visits combined with adjunctive Guided focal Laser photocoagulation to microaneurysms at week 4 and then every 3 months if leakage is present on fluorescein angiography, followed by a treat and extend protocol based on pre-specified criteria of disease activity (GILA cohort, 60 eyes).

Randomization Scheme:

All eyes which satisfy all inclusion/exclusion criteria will be randomized 1:2:2 into the Monthly:TREX:GILA Cohorts.

3 Treatment arms:

1. Monthly Cohort (30 eyes): Monthly intravitreal injections of 0.3 mg ranibizumab for 36 months, unless they meet pre-specified criteria for PRN treatment (indicated below). Treatment will begin at Day 0 and

subsequent study visits should be scheduled to occur every 28 (± 7) days relative to the date of the first injection. Dosing should not occur earlier than 21 days after previous treatments.

Starting at week 104, study eyes will have the opportunity to undergo treatment on a pro re nata (PRN) basis. Thus, eyes who have a central subfield thickness (CST) ≤ 325 microns at the week 104 visit, will not be given treatment at week 104. Eyes will continue to be seen every 4 weeks and will be given an intravitreal injection of ranibizumab 0.3 mg only if the CST is > 325 microns. Eyes will also receive treatment if there is a > 5 letter loss due to DME (compared to the vision at week 104), regardless of thickness on OCT.

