3. GILA Cohort (60 eyes): Monthly intravitreal injections of 0.3 mg ranibizumab for four visits combined with Guided LAser (GILA) photocoagulation to all microaneurysms in the area of DME at the second visit (Week 4). Fluorescein angiography is to be repeated approximately every 3 months (the first visit that occurs ≥ 90 days from the preceding fluorescein angiography visit). Guided laser will be repeated at those visits if leakage is present from microaneurysms.

If the central foveal thickness is $\leq 325 \mu\text{m}$ at Week 12 then the baseline retinal thickness will be recorded, the eye will receive 0.3 mg ranibizumab, and the study eye will begin the extension phase of the study. In the extension phase, appropriate changes to the treatment interval with 0.3 mg ranibizumab (i.e. extend, maintain, reduce) will be made based on pre-specified SD-OCT criteria (SEE TREATMENT INTERVAL DETERMINATION). Treatment is rendered at every visit, no earlier than 7 days before the target date and no later than 7 days after the target date, but the time between visits is individualized based on each subject's response to treatment. Dosing should not occur earlier than 21 days after previous treatments.

If the central foveal thickness is $> 325 \mu\text{m}$ at week 12, then the patient will continue to receive monthly intravitreal injections of 0.3 mg ranibizumab and possible guided laser photocoagulation, approximately every 3 months until the central foveal thickness is $\leq 325 \mu\text{m}$. Once the central foveal thickness is $\leq 325 \mu\text{m}$, then the study eye will begin the extension phase of the study.

Starting at week 104, study eyes will have the opportunity to undergo treatment on a pro re nata (PRN) basis. Thus, eyes who have a central subfield thickness (CST) ≤ 325 microns at the week 104 visit, will not be given treatment at week 104. Starting at week 104, eyes will be seen every 4 weeks and will be given an intravitreal injection of ranibizumab 0.3 mg only if the CST is > 325 microns. Eyes will also receive treatment if there is a > 5 letter loss due to DME (compared to the vision at week 104), regardless of thickness on OCT.

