4.2 METHOD OF TREATMENT ASSIGNMENT

All eyes which satisfy all inclusion/exclusion criteria will be randomized 1:2:2 into the Monthly:TREX:GILA Cohorts. Screening evaluations may be performed at any time within the 14 days preceding Day 0. Randomization will occur at Day 0.

Baseline Measurement For the TREX and GILA cohorts:

Eyes which have a central foveal thickness $\leq 325 \mu\text{m}$ at week 12, a "Primary Baseline" retinal thickness will be defined as the thinnest central foveal thickness on SD-OCT over the first four visits of monthly treatment. Eyes which have a central foveal thickness $> 325 \mu\text{m}$ at week 12 will continue to receive monthly intravitreal injections of 0.3 mg ranibizumab and guided laser photocoagulation every 3 months if leakage is present on fluorescein angiography until the central foveal thickness is $\leq 325 \mu\text{m}$, at which point their "Primary Baseline" retinal thickness will be established.

If at any point in the study period, the study eye has improved more than 20% from the primary baseline thickness for three consecutive visits and there is less than 50 microns of variability in central foveal thickness between these visits, then a "Secondary Baseline" retinal thickness will be established. This "Secondary Baseline" retinal thickness will then be used for treatment interval determinations from that point forward. If the study eye has improved more than 20% from the secondary baseline thickness for three consecutive visits and there

is less than 50 microns of variability in central foveal thickness between these visits, then a “Tertiary Baseline” retinal thickness will be established. This “Tertiary Baseline” retinal thickness will then be used for treatment interval determinations from that point forward.

Treatment Groups:

Monthly Cohort (30 eyes) – Study eyes will receive intravitreal injections of 0.3 mg ranibizumab every 28 days (+/- 7) for 36 months, relative to the date of the first injection (Day 0), unless indicated below.

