TREX Cohort (60 eyes) – Monthly intravitreal injections of 0.3 mg ranibizumab for four visits. At the fourth visit (Week 12), if the central foveal thickness is $\leq 325 \mu\text{m}$ then the eye will receive 0.3 mg ranibizumab and begin the extension phase of the study. For all subsequent visits in the extension phase, appropriate changes to the treatment interval with 0.3 mg ranibizumab (i.e. extend, maintain, reduce) will be made based on pre-specified SD-OCT criteria. Treatment is rendered at every visit, no earlier than 7 days before the target date and no later than 7 days after the target date, but the time between visits is individualized based on each subject's response to treatment. If the central foveal thickness is $> 325 \mu\text{m}$ at week 12, then the patient will continue to receive monthly intravitreal injections of 0.3 mg ranibizumab until the central foveal thickness is $\leq 325 \mu\text{m}$. Once the central foveal thickness is $\leq 325 \mu\text{m}$, then the study eye will begin the extension phase of the study.

Starting at week 104, study eyes will have the opportunity to undergo treatment on a pro re nata (PRN) basis. Thus, eyes who have a central subfield thickness (CST) ≤ 325 microns at the week 104 visit, will not be given treatment at week 104. Starting at week 104, eyes will be seen every 4 weeks and will be given an intravitreal injection of ranibizumab 0.3 mg only if the CST is > 325 microns. Eyes will also receive treatment if there is a > 5 letter loss due to DME (compared to the vision at week 104), regardless of thickness on OCT.

Subjects will be evaluated for focal laser treatment at week 116, week 128, week 140, and week 152. If the subject has received ≥ 2 intravitreal injections of ranibizumab within the prior 90 day period, then fluorescein angiography will be performed and focal laser treatment will be applied to any leaking microaneurysms. If the patient does not meet this criteria for focal laser treatment, then fluorescein angiography and focal laser treatment will be deferred and reassessed at the subsequent laser evaluation visit. Focal laser treatment and focal laser re-treatment will be administered no more than once every 90 days.

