Focal laser therapy will be applied to all leaking microaneurysms on fluorescein angiography. Focal laser therapy will not be applied if significant macular ischemia is present involving the foveal avascular zone (once this has been determined additional fluorescein angiography and focal laser treatment planning should not be performed as the subject will no longer be eligible for focal laser treatment). Focal laser will also not be applied if treatment is considered too close to the foveal avascular zone or to macular edema not related to DME (cystoid

macular edema, etc.). If no microaneurysms are present on fluorescein angiography, then focal laser therapy should be deferred and reassessed with repeat fluorescein angiography at the first visit that occurs after 90 days.

GILA Cohort (60 eyes) – Monthly intravitreal injections of 0.3 mg ranibizumab for four visits combined with Guided LASer (GILA) photocoagulation to all microaneurysms in the area of DME at the second visit (Week 4). Fluorescein angiography is to be repeated approximately every 3 months (the first visit that occurs ≥ 90 days from the preceding fluorescein angiography visit). Guided laser will be repeated at those visits if leakage is present from microaneurysms. If the central foveal thickness is ≤ 325 μm at the fourth visit (Week 12), eyes will receive 0.3 mg ranibizumab and the extension phase will begin. For all subsequent visits in the extension phase, appropriate changes to the treatment interval with 0.3 mg ranibizumab (i.e. extend, maintain, reduce) will be made based on pre-specified SD-OCT criteria. Treatment is rendered at every visit, no earlier than 7 days before the target date and no later than 7 days after the target date, but the time between visits is individualized based on each subject's response to treatment. If the central foveal thickness is > 325 μm at week 12, then the patient will continue to receive monthly intravitreal injections of 0.3 mg ranibizumab and possible guided laser every 3 months until the central foveal thickness is ≤ 325 μm . Once the central foveal thickness is ≤ 325 μm , then the study eye will begin the extension phase of the study.

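### Section 4.2's baseline paragraph for TREX and GILA does not confine guided laser to GILA, contradicting the TREX rule in the same section

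*Combined protocol and SAP*

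**What the plan says.** Section 4.2 has a paragraph headed "Baseline Measurement For the TREX and GILA cohorts". For eyes with central foveal thickness above 325 µm at week 12, it prescribes continued monthly ranibizumab 0.3 mg together with "guided laser photocoagulation every 3 months if leakage is present on fluorescein angiography until the central foveal thickness is" 325 µm or less, when the primary baseline thickness is set. Nothing in the sentence restricts the laser to one cohort.

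The cohort paragraphs later in section 4.2 separate the two arms:

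- **TREX:** such an eye "will continue to receive monthly intravitreal injections of 0.3 mg ranibizumab until the central foveal thickness is" 325 µm or less. No laser is mentioned at this stage. Laser first appears after week 104: "Subjects will be evaluated for focal laser treatment at week 116, week 128, week 140, and week 152".
- **GILA:** such an eye "will continue to receive monthly intravitreal injections of 0.3 mg ranibizumab and possible guided laser every 3 months until the central foveal thickness is" 325 µm or less.

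Section 3.1 follows the same division. It defines GILA as monthly ranibizumab "for 4 visits combined with adjunctive Guided focal Laser photocoagulation to microaneurysms at week 4". Its GILA paragraph gives eyes above the threshold "monthly intravitreal injections of 0.3 mg ranibizumab and possible guided laser photocoagulation, approximately every 3 months until the central foveal thickness is" 325 µm or less, and its TREX paragraph gives injections only. Its own baseline paragraph, and the treatment-interval paragraph after it, state the injections for both cohorts and put the laser in a separate sentence that applies to GILA eyes alone.

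**The concern.** A TREX eye above 325 µm at week 12 with leakage on angiography has two different instructions in one section, and the plan gives no rule for which prevails.

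The disputed treatment is the one that defines the contrast. Before week 104, TREX and GILA share the same injections and the same treat-and-extend rules, and the only planned difference is guided laser with the angiography that guides it. Section 4.8.1 lists TREX versus GILA as the first of three TOST comparisons, paired within 60 patients with bilateral disease, with a stated equivalence boundary of ±7 letters. The primary outcome is at 24 months.

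Laser given to slow-responding TREX eyes would blur that contrast. If laser acts in those eyes in the same direction as it does on average, the observed difference shrinks, which favours a finding of equivalence. If it acts in the opposite direction in that selected subgroup, the difference could widen. The direction of any bias is therefore not fixed.

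**Working it through.** The plan states no figure to reproduce on this point. The check compares texts and then counts the occasions that the literal clause would open.

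**1. The texts side by side, for an eye above 325 µm at week 12**

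| Place | Cohorts covered | Injections | Guided laser before week 104 |
|---|---|---|---|
| 4.2, baseline paragraph | TREX and GILA | monthly | every 3 months if leakage, no cohort limit |
| 4.2, TREX paragraph | TREX | monthly | none; first laser evaluation at week 116 |
| 4.2, GILA paragraph | GILA | monthly | possible, every 3 months |
| 3.1, TREX paragraph | TREX | monthly | none; first laser evaluation at week 116 |
| 3.1, GILA paragraph | GILA | monthly | possible, about every 3 months |
| 3.1, baseline and interval paragraphs | TREX and GILA | monthly | every 3 months if leakage, GILA eyes only |

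The first row is the only one that reaches TREX eyes with laser before week 104.

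**2. Which text is the slip**

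The sentence speaks of continuing laser. Only GILA eyes have had study laser by week 12, because theirs is given at week 4. The clause also closely follows the GILA rule in sections 3.1 and 4.2, and section 3.1's parallel baseline paragraph contains the limit that is missing here. The intended rule for TREX is almost certainly injections only.

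**3. What the literal text would permit**

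- TREX angiograms after screening and through week 104 fall at weeks 12, 52 and 104 (section 3.1; section 4.5.1 gives week 12, month 12 and month 24). Two of these come before week 104: weeks 12 and 52.
- Week 12: any TREX eye above 325 µm with leakage qualifies. This is 116 − 12 = 104 weeks before the first TREX laser evaluation.
- Week 52: the clause lapses once thickness reaches 325 µm or less, so the eye must have been above 325 µm at every four-weekly visit from week 12 to week 52. That is (52 − 12)/4 + 1 = 11 visits.

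On scheduled angiograms, then, there is one occasion, and two at most for an eye that never responds over those 11 visits.

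**4. What cannot be computed**

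An effect in letters would need the share of TREX eyes above 325 µm with leakage at week 12 and the effect of laser in such eyes. The documents give neither, so none is calculated.

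**The case against.** The strongest reply is that a careful reader can recover the rule. The cohort-specific TREX paragraphs in sections 3.1 and 4.2 are unambiguous, and section 3.1 twice limits the laser to GILA. The paragraph at fault exists to define baseline thickness, while treatment by arm follows under its own heading in section 4.2. A three-monthly leakage check does not fit the TREX angiography schedule. All of this stands. It is why the point is minor and why the clause is read as a slip.

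The occasion count can also be challenged. It reads the clause literally but takes the angiograms from the TREX schedule. A fully literal three-monthly reading could give more than two occasions, a contextual reading gives none, and the clause does not name week 12 as a laser visit. That is fair: the count holds only for angiograms already scheduled in TREX. The flowchart in Appendix A is a separate document, so how it sets out laser visits by cohort, and what sites would do in practice, cannot be judged from the text here.

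These arguments do not remove the contradiction. The paragraph names TREX in its heading, contains an operative treatment instruction, and has no qualifier such as an as-applicable clause.

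**Conclusion.** The inconsistency is real and minor. Section 4.2 gives TREX eyes above 325 µm at week 12 two incompatible instructions, and the wrong one permits the treatment that separates GILA from TREX before the 24-month comparison. Its reach is one scheduled occasion per affected eye, or two for an eye that stays above 325 µm throughout weeks 12 to 52. This assumes that laser would be given only at angiograms already planned for TREX. The effect on visual acuity and its direction are unknown. Confidence is high that the texts conflict; nothing in the documents shows that any site would follow the wrong one.

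**What to change.** Replace the sentence in section 4.2 with section 3.1's baseline wording in full. It should state that eyes in either cohort above 325 µm at week 12 go on with monthly ranibizumab until they reach 325 µm or less, when their primary baseline is set. A separate statement should then say that GILA eyes, and only those, go on with guided laser to microaneurysms every 3 months where angiography shows leakage. Carrying over the full wording keeps the definition of the primary baseline, which is the purpose of the paragraph.

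The cost is a one-sentence protocol clarification. It adds no procedure and changes no intended treatment, sample size or power figure.

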4.3 STUDY TREATMENT

4.3.1 Formulation

Ranibizumab is formulated as a sterile solution aseptically filled in a sterile, 3-mL stoppered glass vial. Each single-use vial is designed to deliver 0.05 mL of 6-mg/mL ranibizumab aqueous solution with 10 mM histidine HCl, 10%, α -trehalose dihydrate, and 0.01% polysorbate 20, pH 5.5. This results in the delivery of a 0.3 mg dose of ranibizumab. Each vial contains no preservative and is suitable for single use only.

Further details and molecule characterization will be included in the Investigator Brochure.

4.3.2 Dosage, Administration, and Storage

a. Dosage

Patient will be to receive intravitreal injections of 0.3 mg of ranibizumab.

b. Administration

* *See Appendix B for detailed preparation and administration of ranibizumab injection.

c. Storage

Upon receipt, study drug kits should be refrigerated at 2°C - 8°C (36°F - 46°F). DO NOT FREEZE. Do not use beyond the expiration date. Ranibizumab vials should remain refrigerated. Protect vials from direct light. Store in original carton until time of use.

RANIBIZUMAB VIALS ARE FOR SINGLE USE ONLY. Vials used for one subject may not be used for any other subject.

4.4 CONCOMITANT AND EXCLUDED THERAPIES

Subjects may continue to receive all medications and standard treatments administered for their conditions at the discretion of their treating physician except non-ranibizumab intraocular therapies for DME, including corticosteroids and other anti-VEGF agents.

4.5 STUDY ASSESSMENTS

4.5.1 Assessments during the Treatment Period

See the table of events for the exact assessments at each visit.

Vital Signs (All Study Visits)

Vital signs will include measurements of pulse and systolic and diastolic blood pressure while the patient is in a seated position. Vital signs should be taken before injection of study drug.

Ocular Assessments (All Study Visits)

- Best Corrected Visual Acuity Visual function of the study eye and the fellow eye will be assessed using the ETDRS protocol (The Early Treatment Diabetic Retinopathy Study Group, 1985) at 4 meters. After week 104, a new manifest refraction will be performed at week 116, week 128, week 140, and week 156. The pre-existing refraction will be used to test visual acuity at 4 meters in the intervening visits between weeks 104 and week 156.
- IOP measurement- (perform prior to dilating eyes and post intravitreal injection; the method used for a patient must remain consistent throughout the study). IOP may be measured either by TonoPen or applanation tonometry, but the method of measurement must remain consistent for each patient throughout the study.
- Slit lamp examination- Patient's anterior eye structure and ocular adnexa will be examined at each study visit using a slit lamp by the investigator.
- Indirect Ophthalmoscopy- The patient's posterior pole and peripheral retina will be examined by indirect ophthalmoscopy at each study visit pre dose (bilateral) by the investigator

Ocular Imaging

Fundus Photography and Fluorescein Angiography (FA)

The anatomical state of the retinal vasculature of the study eye will be evaluated by funduscopic examination, fundus photography and FA. Fundus photography and Fluorescein angiography will be done in the Monthly and TREX Cohorts at baseline (screening visit) and again at week 12, month 12, month 24, and month 36. Fundus photography and fluorescein angiography will be done in the GILA Cohort at baseline (screening visit), and again at week 4, and then approximately every three months (first visit that occurs > 90 days from previous fluorescein angiogram). See Appendix A. Fluorescein angiography will be used to guide focal laser treatment for all treatment cohorts at week 116, week 128, week 140, and week 152 if laser treatment criteria has been met.

Optical Coherence Tomography (All Study Visits) –

Ocular morphology will be evaluated using the Heidelberg Spectralis Domain (SD) OCT on the study eye. All SD-OCT images will be captured using the

most current software. All SD-OCTs will be electronically archived at the site as part of the source documentation.

Microperimetry –

Microperimetry will be performed at the locations where a microperimeter is available on all study eyes in the TREX and GILA cohorts at screening, week 24, week 52 and week 104, or the closest visit to these time points.

4.5.2 Early Termination Assessments

Subjects who withdraw from the study prior to completion should return for an early termination evaluation 30 days (± 7 days) following the last injection/study visit for monitoring of all adverse events (serious and nonserious). The schedule of assessments for early termination is the same as that for the final visit.

4.6 SUBJECT DISCONTINUATION

Subjects have a right to withdraw from the study at any time.

The subject may be withdrawn from the study for any reason: if it is in the best interest of the subject, intercurrent illness, adverse events, or worsening condition. Palmetto Retina Center, LLC or [name] may request the withdrawal of a subject because of protocol violations, administrative reasons, or any other valid and ethical reasons.

If a subject discontinues from the study, he or she will not be allowed to re-enter the study.

Reasons for subject discontinuation may include, but are not limited to, the following:

- Sensory rhegmatogenous retinal detachment or Stage 3 or 4 macular hole
- Investigator determination that it is not in the best interest of the subject to continue participation
- Pregnancy
- Need for anti-VEGF therapy other than ranibizumab in the study eye, unless as a part of the prospective investigational study design
- SAE
- Any other safety concerns

In the event of an adverse event in the study eye that is considered by the investigator to be severe in intensity, serious consideration should be given to discontinuing the subject from the study.

